7. SAFETY ANALYSES

7.1. Adverse Events and Deaths

7.1.1. Adverse Event Dictionary

Clinical and laboratory adverse events (AEs) will be coded using the MedDRA 21.0. System organ class (SOC), high-level group term (HLGT), high-level term (HLT), preferred term (PT), and lower-level term (LLT) will be provided in the AE dataset.

7.1.2. Adverse Event Severity

Adverse events are graded by the investigator as Grade 1, 2, 3, 4, or 5 according to toxicity criteria specified in the protocol. The severity grade of events for which the investigator did not record severity will be categorized as “missing” for tabular summaries and data listings. The missing category will be listed last in summary presentation.

7.1.3. Relationship of Adverse Events to Study Drug

Related AEs are those for which the investigator selected “Related” on the AE CRF to the question of “Related to Study Treatment.” Relatedness will always default to the investigator’s choice, not that of the Medical Monitor. Events for which the investigator did not record relationship to study drug will be considered related to study drug for summary purposes. However, by-subject data listings will show the relationship as missing.

7.1.4. Serious Adverse Events

Serious adverse events (SAEs) will be identified and captured as SAEs if AEs met the definitions of SAE that were specified in the study protocol. SAEs captured and stored in the clinical database will be reconciled with the SAE database from the Gilead Pharmacovigilance & Epidemiology Department (PVE) before data finalization.

7.1.5. Treatment-Emergent Adverse Events

7.1.5.1. Definition of Treatment-Emergent Adverse Events

Treatment-emergent adverse events (TEAEs) are defined as one or both of the following:

- Any AEs with an onset date on or after the study drug start date and no later than 30 days after permanent discontinuation of study drug
- Any AEs leading to premature discontinuation of study drug

For placebo subjects who were then re-randomized, TEAEs with an onset date prior to the first dose date of filgotinib will be allocated to the placebo controlled period. TEAEs with an onset date on or after the first dose date of filgotinib will be allocated to the re-randomized period.

7.1.5.2. Incomplete Dates

If the onset date of the AE is incomplete and the AE stop date is not prior to the first dosing date of study drug, then the month and year (or year alone if month is not recorded) of onset determine whether an AE is treatment emergent. The event is considered treatment emergent if both of the following 2 criteria are met:

- The AE onset is the same as or after the month and year (or year) of the first dosing date of study drug, and
- The AE onset date is the same as or before the month and year (or year) of the date corresponding to 30 days after the date of the last dose of study drug

An AE with completely missing onset and stop dates, or with the onset date missing and a stop date later than the first dosing date of study drug, will be considered to be treatment emergent. In addition, an AE with the onset date missing and incomplete stop date with the same or later month and year (or year alone if month is not recorded) as the first dosing date of study drug will be considered treatment emergent.

For placebo subjects who were then re-randomized, an AE with incomplete onset date that is prior to the month and year (or year) of the first dose date of filgotinib will be allocated to the placebo controlled period. An AE with incomplete onset date that is after the month and year (or year) of the first dose date of filgotinib will be allocated to the re-randomized period.

In addition, an AE with completely missing onset date or incomplete onset date that is same as the month and year (or year) of the first dose date of filgotinib, and stop date that is prior to the date (or month and year if day is not recorded; or year alone if month is not recorded) of the first dose of filgotinib will be allocated to the placebo controlled period. An AE with completely missing onset date or incomplete onset date that is same as the month and year (or year) of the first dose date of filgotinib, and stop date that is missing, or the same as, or after the date (or month and year if day is not recorded; or year alone if month is not recorded) of the first dose of filgotinib will be allocated to the re-randomized period.

7.1.6. Summaries of Adverse Events and Deaths

Treatment-emergent AEs will be summarized based on the Safety Analysis Set.

7.1.6.1. Summaries of AE incidence in Combined Severity Grade Subsets

The number and percentage of subjects who experienced at least 1 TEAE will be provided and summarized by SOC, HLT, PT, and treatment group. For other AEs described below, summaries will be provided by SOC, PT, and treatment group:

- TEAEs of Grade 3 or higher (by maximum severity)

- TEAEs of Grade 2 or higher
- All TE treatment-related AEs
- TE Treatment-related AEs of Grade 3 or higher (by maximum severity)
- TE Treatment-related AEs of Grade 2 or higher
- All TE SAEs
- All TE treatment-related SAEs
- All TEAEs leading to premature discontinuation of any study drug
- All TEAEs leading to premature discontinuation of study
- All TE SAEs leading to death (ie, outcome of death)
- All TEAEs leading to temporary interruption of any study drug

A brief, high-level summary of AEs described above will be provided by treatment group and by the number and percentage of subjects who experienced the above AEs. All deaths observed in the study will be also included in this summary.

Multiple events will be counted only once per subject in each summary. Adverse events will be summarized and listed first in alphabetic order of SOC and HLT within each SOC (if applicable), and then by PT in descending order of total frequency within each SOC. For summaries by severity grade, the most severe grade will be used for those AEs that occurred more than once in an individual subject during the study.

In addition to the above summary tables, all TEAEs and TE treatment-related AEs will be summarized by PT only, in descending order of total frequency.

In addition, data listings will be provided for the following:

- All AEs, indicating whether the event is treatment emergent
- All AEs of Grade 3 or higher
- All AEs of Grade 2 or higher
- SAEs
- Deaths
- All SAEs leading to death (ie, outcome of death)

- AEs leading to premature discontinuation of any study drug
- AEs leading to premature discontinuation of study
- AEs leading to temporary interruption of any study drug

7.1.7. Adverse Events of Special Interest

Events of interest will be identified by the use of either SMQs or MSTs. However, should additional cases not detected by the predefined search term listings be identified during the clinical review process, these cases will also be reported by respective category.

7.1.7.1. Adjudication Committee for MACE

An independent cardiovascular safety endpoint adjudication committee (CVEAC) will be formed to periodically review and adjudicate all potential major adverse cardiovascular events (MACE) events. MACE events are defined as cardiovascular death, non-fatal myocardial infarction and non-fatal stroke.

To identify the MACE, the following potential cases identified using MedDRA search term (MST) searches will be adjudicated:

- All deaths
- Cardiovascular events (meeting serious criteria)
- Myocardial infarction (Narrow)
- Hospitalization for unstable angina
- Transient ischemic attack
- Stroke
- Hospitalization for cardiac failure
- Percutaneous coronary intervention

The CVEAC will review those potential MACE and related clinical data to determine whether a MACE has developed. The CVEAC's role and responsibilities and the data to be provided to the CVEAC are described in a mutually agreed upon CVEAC charter. The CVEAC charter defines the CVEAC membership, adjudication process, meeting logistics, and meeting frequency.

The number and percentage of subjects with positively adjudicated MACE will be summarized by treatment group using the PT.

A by-subject listing for all subjects who have potential MACE and who have a positively adjudicated MACE at any time will be provided.

7.1.7.2. Other Adverse Events of Special Interest

In addition to general safety parameters and MACE, safety information on other adverse events of special interest (AESIs) will also be analyzed. AESIs will be identified by laboratory results, standardized MedDRA queries (SMQs), sponsor defined MSTs, or a combination of these methods as indicated below.

- All infections (defined as all PTs in the Infections and Infestations SOC)
- Serious infections (defined as all PTs in the Infections and Infestations SOC that are SAEs)
- Infections of special interest as defined below
 - a) Herpes zoster
 - b) Active tuberculosis
 - c) Opportunistic infections
 - d) Hepatitis B or C infections
- Deep vein thrombosis (DVT) and pulmonary embolism (PE)
- Malignancy (including lymphoma; not including nonmelanoma skin cancer)
- Nonmelanoma skin cancer
- Gastrointestinal (GI) perforations

The number and percentage of subjects with aforementioned events of special interest will be provided by the PT for each AE of special interests.

A by-subject listing for all subjects having AE of special interests at any time will be provided for each AE of special interest.

7.1.8. Additional Analysis for Adverse Events

The number and proportion of subjects who experienced at least one treatment-emergent SAE, or one treatment-emergent AE of special interests will be summarized by treatment group. The comparisons of the proportions between the placebo group during placebo controlled period and the filgotinib treatment groups will be performed. The 2-sided 95% CI of the proportion based on normal approximation with the sample variance will be provided for each treatment group. In addition, the difference in proportions between treatment groups with its 95% CI based on the normal approximation with the pooled sample variance will be provided.

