3.4. Duration of Treatment

Subjects are planned to participate in the study for approximately 60 weeks (from Screening visit to Follow-up visit or entry into the LTE); the duration of dosing is up to 52 weeks.

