8.6. Safety Analysis

All safety analyses will be performed using the safety analysis set.

Safety will be evaluated by assessment of clinical laboratory tests, physical examinations, vital signs measurements at various time points during the study, and by the documentation of AEs.

All safety data collected on or after the first dose of study drug administration up to 30 days after the last dose of study drug, unless specified otherwise, will be summarized by treatment group according to the study drug received.

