1.2. Study Design

This is a randomized, double-blind, placebo- and active-controlled, Phase 3 study in adult male and female subjects with active RA who have an inadequate response to MTX (MTX-IR). The study is designed to evaluate the efficacy, safety, and tolerability of filgotinib as well as its effect on work productivity, fatigue, and quality of life.

Approximately 1650 subjects will be randomized in a 3:3:2:3 ratio to filgotinib 200 mg, filgotinib 100 mg, active comparator (adalimumab), or placebo to match (PTM) administered for up to 52 weeks, all in the context of a weekly stable dose of MTX:

- Filgotinib 200 mg group: filgotinib (200 mg q.d.) + PTM filgotinib 100 mg (PTM q.d.) + PTM adalimumab (PTM s.c. injection q2w) (N=450)
- Filgotinib 100 mg group: filgotinib (100 mg q.d.) + PTM filgotinib 200 mg (PTM q.d.) + PTM adalimumab (PTM s.c. injection q2w) (N=450)
- Active comparator group: PTM filgotinib 200 mg (PTM q.d.) + PTM filgotinib 100 mg (PTM q.d.) + adalimumab (40 mg s.c. injection q2w) (N=300)
- Placebo control group: PTM filgotinib 200 mg (PTM q.d.) + PTM filgotinib 100 mg (PTM q.d.) + PTM adalimumab (PTM s.c. injection q2w) (N=450)

Randomization will be stratified by geographic region, prior exposure to biologic disease modifying antirheumatic drugs (bDMARDs), and presence of rheumatoid factor (RF) or anti-CCP (cyclic citrullinated peptide) antibody (Ab) at screening.

At Week 14, subjects who have not achieved at least 20% improvement from Baseline in both swollen joint count (SJC) and tender joint count (TJC) will discontinue investigational study drug dosing but will continue with study visits and assessments per protocol. All subjects meeting this criterion who discontinue from investigational therapy are to receive standard of care treatment for their RA as determined by the investigator.

[figure not shown]
At Week 24, all subjects assigned to placebo + MTX will be reassigned 1:1 to either filgotinib 100 mg q.d. or 200 mg q.d. in addition to MTX in a blinded fashion and will continue in the study per protocol up to Week 52.

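### The placebo comparison of serious and special-interest adverse events gives filgotinib about twice the time at risk, so equal risks would look roughly doubled on filgotinib

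*SAP*

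**What the plan says.** SAP 7.1.8 (Additional Analysis for Adverse Events) summarizes, by treatment group, "The number and proportion of subjects who experienced at least one treatment-emergent SAE" or at least one event of special interest. It then states: "The comparisons of the proportions between the placebo group during placebo controlled period and the filgotinib treatment groups will be performed". The output includes "the difference in proportions between treatment groups with its 95% CI based on the normal approximation with the pooled sample variance". No cut-off is given for the filgotinib groups.

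The time windows come from elsewhere:

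- **General rule (SAP 7.1.5.1):** an event is treatment-emergent from first dose and "no later than 30 days after permanent discontinuation of study drug". Protocol 8.6 has the same default: safety data "up to 30 days after the last dose of study drug, unless specified otherwise, will be summarized by treatment group".
- **Placebo (SAP 7.1.5.1):** for placebo subjects who are re-randomized, "TEAEs with an onset date prior to the first dose date of filgotinib will be allocated to the placebo controlled period". SAP 1.2 fixes that point: "At Week 24, all subjects assigned to placebo + MTX will be reassigned 1:1".
- **Filgotinib:** Protocol 3.4 says "the duration of dosing is up to 52 weeks". The allocation of events to periods in SAP 7.1.5.1 and 7.1.5.2 is written only for re-randomized placebo subjects.

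The safety sections of both documents contain no patient-year rate and no time-to-event analysis. Exposure is tabulated under SAP 4.2.1 but is never used as a denominator for events.

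**The concern.** A crude proportion with at least one event rises with follow-up. If one arm is counted for 24 weeks and the other for 52 weeks or more, the proportions differ even when the underlying risks are identical.

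The other adverse event summaries are descriptive, so this comparison carries the between-group statement on serious events, infections, herpes zoster, thromboembolism, malignancy and gastrointestinal perforation. The distortion runs against filgotinib. It could produce a false safety signal, and a reader could not tell a real excess from the artefact.

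**Working it through.** The documents give no expected figure for this comparison, so there is none to reproduce. The check asks what the rule would show if the true risk were the same in both arms.

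**Inputs from the documents**
- 450 subjects per filgotinib arm and 450 on placebo (SAP 1.3).
- Placebo window: 24 weeks, to the switch.
- Filgotinib window: 52 weeks of dosing, or 52 + 30/7 = 56.3 weeks with the 30-day tail.
- Window ratio: 52/24 = 2.17, or 56.3/24 = 2.35.

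**Assumptions**
- Equal, constant hazard λ in both arms, so p(t) = 1 − exp(−λt).
- λ of 2, 5 or 10 per 100 patient-years. Protocol 1.2.3 reports serious events over 24 weeks in the Phase 2b methotrexate-combination study at 2.0% (filgotinib) and 4.7% (placebo). Over 168/365.25 = 0.460 years, −ln(0.98)/0.460 = 4.4 and −ln(0.953)/0.460 = 10.5 per 100 patient-years, so 5 and 10 are realistic for serious events.

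**Example at 5 per 100 patient-years, 24 against 52 weeks**
- Placebo: 1 − exp(−0.05 × 0.460) = 2.27%.
- Filgotinib: 1 − exp(−0.05 × 0.997) = 4.86%.
- Ratio 2.14, difference 2.6 points.
- Pooled p̄ = 3.57%; standard error √(2 × 0.0357 × 0.9643/450) = 1.24 points; half-width 1.96 × 1.24 = 2.42 points. The expected difference already exceeds the half-width.

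**Chance that the 95% interval lies wholly above zero with no true effect** (exact binomial enumeration, pooled variance; nominal 2.5% in that direction)

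| Rate per 100 PY | Placebo 24 wk | Filgotinib 52 wk | Ratio | Chance, 52 wk | Chance, 56.3 wk | Chance, 56.3 wk with Week 14 stopping |
|---|---|---|---|---|---|---|
| 2 | 0.9% | 2.0% | 2.15 | 25% | 30% | 18% |
| 5 | 2.3% | 4.9% | 2.14 | 56% | 66% | 44% |
| 10 | 4.5% | 9.5% | 2.11 | 84% | 92% | 72% |

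With the continuity correction of SAP Appendix 8, the 52-week chances at 5 and 10 per 100 patient-years are still about 49% and 81%.

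**Week 14 stopping.** Joint-count non-responders stop study drug at Week 14. The planning ACR20 rates of 45% and 65% imply at most about 55% stopping on placebo and 35% on filgotinib, because ACR20 requires both joint-count responses and more besides. Each stopper is counted to 14 + 30/7 = 18.3 weeks.
- Placebo mean time: 0.45 × 24 + 0.55 × 18.3 = 20.9 weeks.
- Filgotinib mean time: 0.65 × 56.3 + 0.35 × 18.3 = 43.0 weeks.
- Time ratio 43.0/20.9 = 2.06; the ratio of proportions at 5 per 100 patient-years is 2.03.

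**Common events.** For a 24-week risk of 20% or 40%, as might apply to all infections, the ratio is 2.04 or 1.75 with full windows, and 1.82 or 1.59 with Week 14 stopping.

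**After a common 24-week window.** The ratio is 1.00 without stopping and about 1.05 with 55%/35% stopping. Events per patient-year give 1.00 under a constant hazard.

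**The case against.** The strongest reply is that a common window may have been intended. SAP 3.2 lists both filgotinib doses and adalimumab among the groups of the placebo-controlled period, and a group called simply placebo exists only in that period. On that reading the residual ratio is about 1.05. But SAP 3.2 sets no end day for filgotinib subjects, lists the same groups under the re-randomized period as well, and is not invoked in 7.1.8. A programmer applying the written event rules would count filgotinib events to last dose plus 30 days.

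Other points stand in part:

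- **Timing.** The full mismatch belongs to the final analysis. At the Week 24 analysis, filgotinib follow-up depends on accrual, which the documents do not give. With an assumed average filgotinib window of 28 or 36 weeks, the ratio at 5 per 100 patient-years is 1.16 or 1.49, and the chance of a false exclusion of zero about 6% or 17%.
- **Rare events.** At 0.2 or 0.5 per 100 patient-years (assumed, for events such as malignancy), the interval would exclude zero in only about 1% or 7% of trials. The point estimate is still doubled.
- **Placebo window.** Placebo subjects who are not re-randomized are counted to last dose plus 30 days, which could reach about 28 weeks, so 24 weeks is not a strict maximum.
- **Scope.** Efficacy inference and its type I error are untouched, and unequal exposure would be visible in the exposure tables. Filgotinib and adalimumab share the same planned dosing period, so setting those two side by side avoids this mismatch.

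These narrow the size in places. They do not correct the placebo comparison at the final analysis.

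**Conclusion.** The concern holds. Followed as written, SAP 7.1.8 compares crude proportions over unequal windows. For serious events and uncommon events of special interest, equal risks would appear about two-fold higher on filgotinib at the final analysis: ratios of about 2.0 to 2.3, falling to about 1.6 to 2.0 for common events. At 5 per 100 patient-years, an interval wrongly excluding zero would be expected in roughly 44% to 66% of trials, depending on Week 14 stopping and the 30-day tail.

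This rests on constant and equal hazards, 450 per arm, and the plain reading that the period limit applies to placebo only. If a common window was intended, the SAP does not define it and still needs the change. Because this is the only planned between-group inference on adverse events, it should be corrected before unblinded results are produced.

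**What to change.** In SAP 7.1.8, state that all arms are compared over the same placebo-controlled window. Count each subject's events to the earliest of last dose plus 30 days, first filgotinib dose after re-randomization, or a defined Week 24 study day, and apply that end day to the filgotinib and adalimumab groups as well as placebo.

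Add exposure-adjusted incidence: subjects with a first event per 100 patient-years at risk, with rate differences and 95% confidence intervals, both for that window and for the whole study. The rates also deal with the residual imbalance from unequal Week 14 stopping.

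The cost is SAP wording and a few extra tables from dates already collected. Trial conduct and the efficacy testing hierarchy are unaffected.

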A total of 15 subjects had ≥ 1 serious TEAE; 4 subjects in the placebo group (4.7%) and 11 subjects (2.0%) in one of the filgotinib groups. One of these subjects with ≥ 1 serious TEAE, who received filgotinib 100 mg twice daily with concurrent MTX, died during the second 12 weeks of the study period due to pneumonia and septic shock. Out of the 15 subjects with a serious TEAE, 11 subjects had a serious TEAE due to which the study medication was stopped and the subject discontinued the study. A total of 23 subjects had ≥ 1 AE leading to permanent discontinuation of the study medication and the study; 2 subjects (2.3%) in the placebo group and 21 subjects (3.9%) in one of the filgotinib groups (including a subject in the filgotinib 100 mg q.d. group who had a pre-dosing AE which was ongoing throughout the study, for which the study medication was permanently discontinued). Most of the serious TEAEs and the AEs leading to discontinuation (by preferred term) were experienced by a single subject.

For the duration of the study, the most common ($\geq 10\%$) TEAEs reported by SOC in subjects from both the placebo and filgotinib dosing groups, were Infections and Infestations and Gastrointestinal disorders. There were no differences between subjects who received placebo or filgotinib in the severity of TEAEs (most TEAEs were mild or moderate; severe TEAEs were observed in 1.2% of “All Placebo Exposed” subjects and in 2.2% of “All filgotinib Exposed” subjects). Treatment-related TEAEs were generally reported more often for subjects in the filgotinib dosing groups than in the placebo group (9.3% with placebo and 20.3% with filgotinib); however, within the different filgotinib dosing groups, no clear dose relationships were observed.

Six serious infections were reported (1 in placebo arm, 5 in filgotinib arm). All 6 serious and one additional non-serious infection in the filgotinib group led to dosing discontinuation. Up to Week 24, herpes zoster infections were observed in 5 subjects (1 placebo treated patient and 4 filgotinib). No cases of tuberculosis, opportunistic infections, lymphoma, or cancer were reported throughout the 24-week dosing period.

Laboratory data were consistent with prior phase 2 studies and no new safety findings were observed from laboratory data. A summary of laboratory findings of interest, including hemoglobin, neutrophil, lymphocyte, creatinine, lipid, and hormone data are summarized below.

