During the whole study, the most common TEAEs reported by System Organ Class in subjects from both the placebo and filgotinib treatment groups, were ‘Infections and Infestations’ and ‘Gastrointestinal disorders’. There were no differences between subjects who received placebo or filgotinib in the severity of TEAEs (most TEAEs were mild or moderate; severe TEAEs were observed in 1.4% of “All Placebo Exposed” subjects and in 1.1% of “All filgotinib Exposed” subjects). Treatment-related TEAEs were generally reported more often for subjects in the filgotinib treatment groups than in the placebo group (9.7% with placebo and 16.7% with filgotinib); however, within the different filgotinib treatment group, no clear dose relationships were observed.

Low numbers of infections were reported as serious (4 subjects with filgotinib) or led to discontinuation of the study medication (2 serious infections; ie, cellulitis and pneumonia) were observed during the study. Up to Week 24, 1 subject (filgotinib 50 mg q.d. group) had a herpes zoster infection. No cases of tuberculosis, opportunistic infections, lymphoma, or cancer were reported throughout the 24-week treatment period.

Laboratory data were consistent with prior studies and no new safety findings were observed.

Please refer to the IB for additional data regarding efficacy and safety.

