6.2.3. Primary Analysis of the Primary Efficacy Endpoint

To test for superiority of filgotinib 200 mg group versus placebo control group in proportion of subjects who achieve ACR20 at Week 12, a logistic regression analysis with treatment groups and stratification factors in the model will be used. The model will include all treatment groups. Subjects who do not have sufficient measurements to establish efficacy at Week 12 will be considered as failures (ie, NRI). The p-value from the logistic regression model for testing the superiority of filgotinib 200 mg as compared to placebo will be provided. The 2-sided 95% confidence interval (CI) of the ACR20 response rate at Week 12 based on normal approximation with the sample variance will be provided for each treatment group. In addition, non-stratified ACR20 response rate difference along with its 95% CI calculated based on the normal approximation with the pooled sample variance will be provided. [Appendix 8](#) provides samples SAS model statements for constructing the confidence interval for the proportion.

The comparisons of filgotinib 100 mg groups versus placebo group in the proportion of subjects achieving ACR20 at Week 12 will also be conducted with the similar logistic regression model with NRI as aforementioned.

The number and percentage of ACR20 non-responders observed and non-responders due to missing at Week 12 will also be summarized respectively by treatment.

For subjects with observed ACR20 outcomes (ie, responders and observed non-responders) at Week 12, actual values and change from Baseline at Week 12 in individual components, including TJC68, SJC66, SGA, PGA, Subject's pain assessment, hsCRP, will be summarized using descriptive statistics (sample size, mean, SD, median, Q1, Q3, minimum, and maximum) by treatment.

The proportions of subjects achieving ACR20 (using NRI) will be plotted over time from Baseline through Week 24 by treatment and by visit.

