Appendix 8. Sample SAS Code for Analysis of Binary Endpoints

The following model statement will be used to construct the confidence interval for the binomial proportions described in Sections 6.2.3, 6.3.2 and 6.4.2:

```
proc freq data = test ;  
  by avisitn;  
  tables TRT01PN*aval_ / riskdiff (CORRECT);  
  output out = f200vp ci RISKDIFF;  
  where TRT01PN = 1 | TRT01PN = 3;  
run;
```

where the confidence interval for the difference of two independent binomial proportions is constructed based on the normal approximation (ie, the Wald method) with continuity correction, to adjust for the difference between the normal approximation and the binomial distribution, which is a discrete distribution:

$$(\hat{p}_1 - \hat{p}_2) \pm \left(\frac{1}{2} \left(\frac{1}{n_1} + \frac{1}{n_2} \right) + z_{\alpha/2} \times \sqrt{\frac{\hat{p}_1(1 - \hat{p}_1)}{n_1} + \frac{\hat{p}_2(1 - \hat{p}_2)}{n_2}} \right)$$

and the confidence interval for the binomial proportions is constructed based on the normal approximation to the binomial distribution with continuity correction:

$$\hat{p}_1 \pm \left(\frac{1}{2n_1} + z_{\alpha/2} \times \sqrt{\frac{\hat{p}_1(1 - \hat{p}_1)}{n_1}} \right)$$

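### SAP 7.1.8 prescribes normal-approximation confidence intervals for SAE and AESI risks; these have zero width at zero events and fall well short of 95% coverage at very low risks

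*SAP*

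**What the plan says.** SAP Section 7.1.8 summarises the number and proportion of subjects with a treatment-emergent SAE or a treatment-emergent AESI and compares filgotinib with placebo. For each group: "The 2-sided 95% CI of the proportion based on normal approximation with the sample variance will be provided for each treatment group". For the comparison: "the difference in proportions between treatment groups with its 95% CI based on the normal approximation with the pooled sample variance will be provided". It gives no formula or code, and no fallback for small counts.

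SAP Section 7.1.7.2 lists the AESIs. They include active tuberculosis, opportunistic infections, hepatitis B or C, DVT and PE, malignancy, nonmelanoma skin cancer and GI perforation, alongside the common category of all infections. It adds: "The number and percentage of subjects with aforementioned events of special interest will be provided by the PT for each AE of special interests".

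Appendix 8 is the only place that prints interval formulas, and it defines its own scope: "The following model statement will be used to construct the confidence interval for the binomial proportions described in Sections 6.2.3, 6.3.2 and 6.4.2". Section 7.1.8 is not among them. The difference interval there is "constructed based on the normal approximation (ie, the Wald method) with continuity correction", with a separate variance for each arm. The efficacy text in Section 6.2.3 says otherwise: "non-stratified ACR20 response rate difference along with its 95% CI calculated based on the normal approximation with the pooled sample variance will be provided". Sections 6.2.4.1, 6.3.2 and 6.4.2 also specify pooled variance.

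**The concern.** The normal-approximation interval takes its width from the estimated variance. When no event is seen that variance is zero, so the interval collapses to a point. With one to three events the lower limit is negative and the upper limit, which matters most for safety, is too low.

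Such counts are foreseeable. Protocol Section 1.2.3 says of study GLPG0634-CL-203: "No cases of tuberculosis, opportunistic infections, lymphoma, or cancer were reported throughout the 24-week dosing period". It reports the same for GLPG0634-CL-204. If intervals are produced by AESI category, a group with no cases would be shown as 0% to 0%, and a comparison of none with none as a difference of 0 to 0. Both read as certainty, although 450 subjects without a case cannot exclude a risk near 0.8%.

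The efficacy point is smaller: the text and the printed formula cannot both be followed.

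**Working it through.** **Inputs.** Group sizes come from SAP Section 1.3: 450 for each filgotinib dose and placebo, 300 for adalimumab. A placebo-switch group can hold at most 450/2 = 225. The SAP states no coverage figure for 7.1.8. The group size itself reproduces: 2 × (1.960 + 1.282)² × 1.85² / 0.4² = 449.5, so 450, with power 90.0%. True AESI risks are my assumption, because the documents give no design value.

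**One group.** Prescribed: p ± 1.96 × √(p(1−p)/n). Exact (Clopper-Pearson) upper limit at zero events: 1 − 0.025^(1/n).

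| Events / n | Prescribed 95% CI | Exact 95% CI |
|---|---|---|
| 0/450 | 0 to 0% | 0 to 0.82% |
| 1/450 | -0.21 to 0.66% | 0.01 to 1.23% |
| 3/450 | -0.09 to 1.42% | 0.14 to 1.94% |
| 0/300 | 0 to 0% | 0 to 1.22% |
| 0/225 | 0 to 0% | 0 to 1.63% |

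For example, at 1/450, p = 0.222% and the half-width is 1.96 × √(0.00222 × 0.99778/450) = 0.435%.

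**Coverage of one group's interval**, by summing binomial probabilities over every count whose interval contains the true risk:

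| Assumed risk | Chance of 0 in 450 | Prescribed, n=450 | Exact, n=450 | Prescribed, n=300 |
|---|---|---|---|---|
| 0.1% | 64% | 36% | 99% | 26% |
| 0.2% | 41% | 59% | 99% | 45% |
| 0.5% | 10% | 89% | 99% | 78% |
| 1% | 1% | 93% | 97% | 80% |
| 2% | 0% | 94% | 96% | 93% |

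**Are such risks plausible?** Protocol Section 1.2.3 gives 21 filgotinib subjects as 3.9% and 8 as 2.9%, implying about 21/0.039 = 538 and 8/0.029 = 276 exposed, 814 in all. No case of tuberculosis, opportunistic infection, lymphoma or cancer in 814 has an exact upper limit of 1 − 0.025^(1/814) = 0.45%. Risks of 0.1% to 0.5% are therefore compatible with Phase 2b or close to its upper limit.

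**Difference, 450 per group.** Prescribed: d ± 1.96 × √(p̄(1−p̄)(1/n₁+1/n₂)). Comparator: Miettinen-Nurminen score interval. In percentage points:

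| Events | Pooled | Score |
|---|---|---|
| 0 v 0 | 0 to 0 | -0.85 to 0.85 |
| 1 v 0 | -0.21 to 0.66 | -0.63 to 1.25 |
| 3 v 0 | -0.09 to 1.42 | -0.18 to 1.94 |

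Coverage by double binomial sums, pooled then score: 0.2% v 0.1%, 74% and 99.8%; 0.5% v 0.1%, 89% and 98%; 1% v 0.1%, 93% and 93%. At equal risks both methods give 99.8% (0.1% v 0.1%) and 95.6% (0.5% v 0.5%).

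**Would Appendix 8's correction repair 7.1.8?** Adding 1/(2n) turns 0/450 into -0.11% to 0.11%. Coverage at 0.1% rises to 100%, but stays 59% at 0.2% and 89% at 0.5%.

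**Efficacy formulas.** At the planning rates of 65% v 45%, 450 per group, the half-widths in points are:

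- pooled, as in 6.2.3: 1.96 × √(0.55 × 0.45 × 2/450) = 6.50
- unpooled: 1.96 × √((0.65 × 0.35 + 0.45 × 0.55)/450) = 6.37
- Appendix 8: 6.37 + 0.22 = 6.59

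**The case against.** The strongest reply is that 7.1.8 may mean only two proportions per group, any SAE and any AESI. Any AESI includes all infections and cannot be rare, and Phase 2b SAE risks were 1.4% to 4.7%. The sentence in 7.1.7.2 promises counts and percentages by category, not intervals. This stands as a limit: on that reading zero counts are unrealistic and the loss is modest. It is not nil, since coverage at n=450 is 90%, 94% and 91% at SAE risks of 1.5%, 2% and 3%. Because 7.1.7.2 treats each AESI separately, the by-category reading is realistic and the SAP should settle it.

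Other points are also fair. At 0.1% and 0.2% the undercoverage is essentially the chance of a zero count, so it restates the zero-width defect. The difference interval is near nominal or conservative when the two risks are equal. The Protocol's Phase 2b summary gives no counts for DVT/PE or GI perforation, so the evidence for near-zero counts covers only some categories. Safety lies outside the testing hierarchy, and counts and listings will show 0/450 directly. None of this makes a 0% to 0% interval, or an upper limit of 0.66% after one event, a valid 95% statement.

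**Conclusion.** The concern holds. As written, 7.1.8 gives zero-width intervals at zero events, impossible lower limits and too-low upper limits at one to three events, and single-group coverage of 36% to 89% at risks of 0.1% to 0.5% with 450 subjects. With 300 subjects the shortfall extends to 1% (80%). This rests on assumed true risks, and its full force depends on intervals being given by AESI category. It does not touch common categories. The difference interval fails at 0 v 0 and when both risks are very low and unequal.

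The pooled versus unpooled conflict is real but is a reporting inconsistency. Half-widths span 6.37 to 6.59 points, and the primary p-value comes from logistic regression, so the primary conclusion is unaffected.

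**What to change.** 1. In Section 7.1.8, specify Clopper-Pearson intervals for each group's proportion and Miettinen-Nurminen score intervals for differences. State whether they are given for each AESI category or only for any AESI.
2. Align Sections 6.2.3, 6.3.2 and 6.4.2 with Appendix 8 on one unpooled formula. State the continuity correction in both places or remove it from both. Apply the same formula to Section 6.2.4.1, which Appendix 8 does not list.

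The cost is SAP wording and standard software options, with no data, subjects or alpha. The price is somewhat wider intervals: the exact single-group intervals are conservative, covering 96% to 99% at risks of 0.1% to 2% with 450 subjects. The score interval is not uniformly better (both methods cover 93% at 1% v 0.1%), but it removes the zero-width result and the worst undercoverage.
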